Any changes, updated and/or new study materials should be uploaded and questions 19 - 24 of this form should be completed.

1. Please indicate the status of the study:

- a) The study has not started but will become active.
Please explain why the study has not started.
- b) The study is ACTIVE (please check the appropriate box below):
Study is open to accrual.
Study is on hold or halted.
Please explain what needs to occur before accrual can resume.
- Study is permanently closed to accrual.
- i. Have all subjects completed all research related

Protocol Title: Natural Procreative Technology Evaluation and Surveillance of Treatment for Infertility and Miscarriage

- activities/interventions?
- ii. N Will the research only remain active for long-term follow-up of subjects?
 - iii. Y Are remaining research activities limited to data analysis only? (See instructions above).
 - iv. N For studies that are closed to subject accrual, do any subjects need to be re-consented (to inform them about changes to study procedures, study risks, study personnel, etc.)?

For IRB office use: * may qualify for expedited review

- c) The study has expired and needs to be re-initiated.
Explain any research activities occurring during lapse in IRB approval.

2. Date the study was initially approved by the IRB: 01/20/2016
3. Approval date of previous continuing review: 01/08/2019
4. Total number of participants/records/specimens you are approved to enroll. 600 participants (300 women and 300 partners)
5. Total number of subjects that have given consent (verbal or written) to date. 72 (45 women + 27 male partners)
6. Total number of subjects that failed screening (if not applicable, state N/A). 0
7. Total number of participants accrued since the beginning of the project. 72 (45 women + 27 male partners)
8. For multi-center studies, number of subjects approved for accrual study-wide (SLU site plus all other sites). N/A
9. For multi-center studies, number of subjects enrolled study-wide (SLU site plus other sites). N/A
10. Number of withdrawals from the research and explanation/reasons for withdrawals. None

Protocol Title: Natural Procreative Technology Evaluation and Surveillance of Treatment for Infertility and Miscarriage

11. Description and number of:

a) Reportable Protocol Deviations/Violations since the last approval date:

None

b) Unanticipated Problems (UPs) since the last approval date:

None

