Infertility is a common problem. While most of current clinical research of infertility focuses on in vitro fertilization and related techniques of assisted reproductive technology (ART), some couples do not wish to use in vitro fertilization, or cannot afford it. Natural procreative technology (NPT) is a standardized approach to the treatment of infertility that does not involve ART. NPT incorporates standard infertility treatments (such as clomiphene or progesterone) within a set of standardized application protocols. The goal of NPT is to identify abnormalities of the woman's reproductive cycle (menstrual cycle), and where possible, correct them by medical intervention.(1, 2) An integral part of NPT is teaching women to observe and chart the biomarkers of their fertility (menstrual) cycle, based on changes in vaginal discharge (resulting from uterine bleeding and cervical mucus production). This charting of fertility biomarkers is done according to the Creighton Model FertilityCare System (CrM). (3) The CrM has several applications. First, the CrM chart alerts women when ovulation is approaching within the next few days and therefore intercourse is most likely to result in pregnancy, even for subfertile couples.(4, 5) Second, it also gives the physician a record that can be used as a standardized basis for doing diagnostic tests timed in reference to ovulation. Third, the physician can also employ standard medications to enhance ovulation, luteal hormonal production, or cervical mucus production, and use the CrM chart to assess the immediate response of the woman to treatment. Where appropriate, NPT may also include medical treatment for male factor infertility, and for prior miscarriage. Formal evaluation of the outcomes of NPT in medical practice has been limited to a few studies based on single medical practices.(6-9) We plan to conduct a prospective observational study to measure the generalizability of this program to multiple populations and settings, and characteristics of patients that may correlate with the likelihood of treatment success.

Please save frequently

- b) Describe any animal experimentation and findings leading to the formulation of the study, if there is no supporting human data.

NA

2. Purpose of the study

- a) Provide a brief lay summary of the project in <200 words. The lay summary should be readily understandable to the general public.

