This is a prospective cohort observational study. Couples presenting for possible treatment with NPT will be recruited for participation in the study. No randomization will occur. If a couple agrees to participate, we will collect information in three ways:

1) Questionnaires. (This is standard of care) These will be done at entry (SOC) to the study, on an annual basis for up to three years (research related), for any pregnancy, or whenever a patient exits the study. Questionnaires may be done by mail, email, or telephone. Each questionnaire has a woman's and a man's version, except the pregnancy questionnaire, which only has a woman's version. Each questionnaire will take approximately 30-45 minutes to complete.

2) The subject's own Creighton Model fertility charts. (standard of care)

3) Information about NPT treatment and pregnancies from the medical records of their NPT physician(s). (standard of care)

d) If subjects will be given placebo, please justify placebo use. *?HELP?*

NA

3. Study Procedures

a) N Is this project a multicenter study (i.e., same project is conducted elsewhere by a different investigator) OR does this study involve conduct of research at multiple sites?

Is SLU acting as a coordinating center for other sites OR is the SLU PI a direct recipient of a federal grant for this research? If yes, complete and attach the Supplemental Application for Coordinating Center Activities.

Will the SLU site be participating in all parts/procedures/arms of the study?

If No, explain what SLU will NOT participate in:

Please save frequently

Protocol Title: Natural Procreative Technology Evaluation and Surveillance of Treatment for Infertility and Miscarriage

Page numbers from a sponsor's protocol/grant may be referenced in 3b, 3c, and 3d.

- b) Describe all the procedures, from screening through end-of-study, that the human subject must undergo in the research project, including study visits, drug treatments, randomization and the procedures that are part of standard of care. Specify which procedures are for research and which are standard of care. Please note: The box below is for text only. If you would like to add tables, charts, etc., attach those files in the Attachment section (#16).

The clinical care will be performed as usual, and will not be altered by this study. If a couple agrees to participate, we will collect information from them in three ways:

1)

For women:

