The sample size is not exact since its size depends upon the total number of patients seen at the participating clinic. We do not have sufficiently reliable information to estimate the variance of the predictor variables (age, prior pregnancy, associate medical diagnoses, and other characteristics) in predicting the primary outcome of live birth. Because this is an observational study of existing treatment, we will conduct interim analyses yearly.

Please save frequently

- e) State if deception (including incomplete disclosure of study purpose/procedures) will be used. If so, describe the nature of the deception and provide a rationale for its use. Also, describe debriefing procedures or justify a waiver of the requirement to debrief. NOTE: for studies using deception, an alteration of consent must be justified in the Informed Consent section of the protocol (#13) and the debriefing script/statement must be uploaded in the Attachments section (#16). See IRB Deception Guidelines.
- f) Is there an accepted standard of care and/or standard practice at SLU for the condition/disease/situation being studied? This information will assist in comparing the risk/benefit ratio of study procedures relevant to usual care that would be received outside of the research context. *?HELP?* Y

If yes, please describe the standard of care and standard practice at SLU for the condition/disease/situation being studied.

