*** Subject Population ***

8. Subject Population - In the space below, please detail the participants that you are requesting to recruit

Protocol Title: Natural Procreative Technology Evaluation and Surveillance of Treatment for Infertility and Miscarriage

(include description of each group requested)

- a) **Expected age range of subjects. (For example ≥ 18 yrs to 90 yrs).**

18-55yrs of age

- b) **Number of evaluable subjects to be accrued at SLU or SLU site (this includes all sites under the direction of the SLU PI).**

600 participants (300 women and 300 partners)

Exceeding the number listed here is a protocol violation. Prior IRB approval is required if additional participants are to be accrued. If applicable, this number should be consistent with your power analysis described in 3d.

- c) **Number of evaluable subjects to be accrued study wide. *?HELP?***

600 participants (300 women and 300 partners)

- d) **If including vulnerable populations (minors, pregnant women and fetuses, neonates, non-English speaking, economically or educationally disadvantaged, prisoners, adults temporarily or permanently unable to consent for themselves): 1) provide the rationale for the importance of including this population in the research, and 2) specify the measures being taken to minimize risks to potentially vulnerable subjects. Click on hyperlinks to access SLU Guidelines containing additional considerations and strategies for mitigating risks.**

NA

- e) **If women, minorities, or minors are not included, a clear compelling rationale must be provided unless not applicable. Examples for not including minors: disease does not occur in children; drug or device would interfere with normal growth and development; etc. If federally funded reference appropriate section of the sponsors protocol/grant. *?HELP?***

Women and minorities are included. Usually minors are not seen for infertility

- f) **If any specifically targeted subjects are students, employees, or laboratory personnel, specify the measures being taken to minimize the risks and the chance of harm to these potentially vulnerable subjects. See SLU Guidelines for additional considerations and strategies for mitigating risks.**

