- g) **Describe (labeled a-c): a) who you are recruiting for this study (e.g., your patients/students/colleagues, those in existing database or registry, the general public), and b) how you are recruiting (flyers, advertisements, direct call/mailing, membership networks, in-person recruitment in clinic, classroom, public locations, etc.). For secondary data analysis or specimen studies, state how you have access to materials. Importantly: do not contact participants prior to obtaining IRB approval for your study.**

c) **Also indicate whether or not you plan to obtain personal/private information or biospecimens for the purpose of screening, recruiting, or determining eligibility of prospective subjects prior to obtaining informed consent and how (obtained by communicating with prospective subjects or obtained by accessing records or stored biospecimens). Note: if you are accessing medical records other than those of your own patients or those in your immediate department, you will need to submit a HIPAA Preparatory to Research form and submit to the SLU Privacy Officer PRIOR to accessing records.**

Protocol Title: Natural Procreative Technology Evaluation and Surveillance of Treatment for Infertility and Miscarriage

Please refer to the SLU IRB Recruitment Guidelines when designing recruitment strategies and upload recruitment materials to the Attachments page for IRB review. You are expected to obtain permission for individuals/organizations that assist with recruitment, and whenever possible, those assisting should share your materials with potential participants on your behalf rather than providing you with private contact information.

Couples seeking NPT treatment or consultation to achieve pregnancy, to maintain pregnancy, or for fertility-related health issues will be recruited from our practice. Providers will present the study information to the patients at any visit. Women and their partner do not have to be consented at the same visit on the same date. No recruitment by phone or mail will be done.

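### Section 1a promises to measure generalizability across settings, but the study is confined to one practice; separately, with at most 45 women, the exploratory Cox models may give no finite hazard ratio for an uncommon diagnosis

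*Combined protocol and SAP*

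**What the plan says.** **Purpose.** Section 1a (Background) says that formal evaluation of NPT outcomes "has been limited to a few studies based on single medical practices". It then gives the aim of this study as to "measure the generalizability of this program to multiple populations and settings", along with patient characteristics that may relate to treatment success.

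**Number of practices.**
- Section 3a answers no to the question on multicenter or multi-site conduct: "N Is this project a multicenter study".
- Section 3d (Sample Size) says the size "depends upon the total number of patients seen at the participating clinic", in the singular.
- Section 8g says couples "will be recruited from our practice".
- Sections 8b and 8c give the same figure, 300 women and 300 partners, for the local site and study wide.
- Item 9 of the continuing review form reads "number of subjects enrolled study-wide (SLU site plus other sites). N/A".

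**Women available.** Items 5 and 7 of that form give 72 participants, 45 women and 27 male partners. Item 1 says only data analysis remains. Item 13 says that nobody has enrolled since the previous review and that follow-up is finished.

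**Analysis.** Section 3d plans life tables for live birth and exploratory Cox regression on woman's age, prior pregnancy and associated diagnoses, and repeats both for conception. It names no method for a factor level with few or no events. Section 2b lists underlying diagnoses among the characteristics of interest and calls the study exploratory.

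**The concern.** There are two separate problems.

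First, the stated rationale and the design disagree. The study shares the limitation that section 1a attributes to earlier work. A manuscript is in preparation, so the sentence in 1a could carry into its conclusions, and a one-practice result could be read as having filled the gap.

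Second, the Cox models were planned under a ceiling of 300 women, and at most 45 exist. In a sample that small, an uncommon diagnosis may have no live birth among the women who have it. The ordinary Cox estimate for that diagnosis then runs off to zero, and the plan does not say what is reported in that case.

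**Working it through.** **1. One practice or several.** Section 1a speaks of multiple populations and settings. Section 3a says not multi-site, 3d says one clinic, 8g says one practice, 8b and 8c give identical local and study-wide numbers, and the continuing review form enters N/A for other sites. Section 3d contains no analysis by setting. With one setting there is no between-setting variation to estimate, whatever the number of women.

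**2. Counts.** 45 + 27 = 72 and 300 + 300 = 600, as stated. 45/300 = 15% of the approved number of women. The documents give no power or precision calculation behind the 300, so there is none to reproduce.

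**3. Why zero events matters.** Each live birth contributes exp(βx) divided by the sum of exp(βx) over the women still at risk. If no woman with the diagnosis (x = 1) has a live birth, β appears only in the denominators. The partial likelihood then keeps rising as β falls, and no finite maximum exists. This holds even for a one-factor model.

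**4. How likely that is.** The documents give neither a live-birth rate nor a diagnosis prevalence. Assumptions: 20%, 40% or 60% of 45 women have a live birth, so D = 9, 18 or 27; the diagnosis is held by k = 5 or 9 of 45; no woman is censored before the last event.

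- Diagnosis unrelated to live birth: P = C(45 − k, D) / C(45, D).
- True hazard ratio 0.5: P = product over i = 0 to D − 1 of (45 − k − i) / (45 − k − i + 0.5k). Each factor is the chance that the next live birth falls to a woman without the diagnosis.

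| | D = 9 | D = 18 | D = 27 |
|---|---|---|---|
| k = 5, unrelated | 30.9% | 6.6% | 0.7% |
| k = 5, HR 0.5 | 54% | 24% | 7% |
| k = 9, unrelated | 10.6% | 0.5% | 0.005% |
| k = 9, HR 0.5 | 30% | 6% | 0.4% |

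For comparison, at 300 women with the same 11% prevalence (33 women) and 60 live births, the unrelated case gives C(267, 60)/C(300, 60) = 0.04%. In a model with several factors these chances are lower bounds on a non-finite fit, because other factors can also fail.

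**5. What stays estimable.** With no live birth among k women, the exact 95% interval for the proportion runs from 0 to 1 − 0.025^(1/k): 0 to 52% for k = 5 and 0 to 34% for k = 9. Life tables by diagnosis can also still be drawn.

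**6. What Firth penalisation does.** A four-factor simulation used age (HR 0.75 per SD), prior pregnancy (50% of women, HR 1.3), a diagnosis in 5 of 45 (HR 0.5) and a second diagnosis (25%, HR 1), all assumed. The Firth estimate was finite in every run. Its average for the true 0.5 (geometric mean) was roughly 0.7 to 0.8 at 9 live births and 0.5 to 0.6 at 18 and at 27. It was more than twofold off in about half of the runs at 9 and 18 live births, and in about 31% at 27.

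**The case against.** **The generalizability phrase is only background.** It is absent from the 2b objectives, no analysis in 3d depends on it, and one more practice does add a setting to those already studied. All of this stands. A reader might infer that the study tells us nothing beyond earlier work, and the documents do not support that. What they support is narrower: one practice cannot measure variation across settings, and 1a says the study will measure generalizability.

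**The Cox problem is conditional.** Event count, diagnosis prevalence and number of terms are not in the documents, and 3d does not say whether the models have one factor or several. This stands too. The larger figures combine few live births with an uncommon diagnosis, and the risk nearly vanishes at 27 live births with 9 women holding the diagnosis. The documents therefore do not show that a sparse-event fit is required.

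**The diagnosis aim survives without Firth.** A reader might infer that the 2b aim could be left with nothing to report. It could not: that aim concerns live-birth rates and how they vary, and life tables and proportions with intervals still give rates by diagnosis.

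**Firth does not give a precise answer.** Correct: it gives a finite estimate with an interval, shrunk toward 1 and wide. For conception the case is no stronger than for live birth, because at least as many women conceive as have a live birth.

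**Conclusion.** The wording conflict in section 1a is established by the text and rests on no assumption. The limit of 45 women is also documented.

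The Cox point is a conditional risk. For a diagnosis held by 5 of 45 women, the chance of a non-finite hazard ratio from zero events runs from about 31% down to 0.7% if the diagnosis is unrelated to live birth, and from about 54% down to 7% at a true hazard ratio of 0.5, as live births rise from 9 to 27. These figures rest on the assumed live-birth rates, prevalence and absence of early censoring. What is exposed is the hazard ratio for such a diagnosis, not the estimation of live-birth rates by diagnosis.

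A reader might also infer that the study missed a powered target by reaching 15% of 300. The documents do not support that: 300 is an approved ceiling, section 3d says the size is not exact, and no power claim is made.

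**What to change.** 1. Reword section 1a as estimating live-birth rates, and the patient characteristics associated with them, in one practice. Draw no conclusion about generalizability across settings in the report.
2. In section 3d, fit the exploratory Cox models with Firth penalisation and profile-likelihood confidence intervals, keep diagnoses in the models, and label the choice as made after follow-up ended.
3. Whatever fit is used, report for each diagnosis the event count, the numbers at risk, and the live-birth proportion or life-table estimate with its confidence interval.

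**Cost.** A narrower stated scope, one fitting option and one extra table; no new data. Firth hazard ratios are shrunk toward 1 and remain imprecise, so the wide intervals must be shown and the point estimates not read alone.

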This study involves research, and the purpose of this study is to evaluate live birth rates among couples who are treated by Natural procreative technology, (NPT) for infertility and miscarriage.

Comparisons will be made to those declining NPT treatment, waiting for NPT treatment, receiving other treatment, or stopping treatment. We seek to document specific pregnancy rates for different factors such as age and type of infertility diagnosis. We will also assess characteristics of environmental exposures that may be associated with infertility. Couples will be followed for up to three years, regardless of when they begin NPT treatment, or whether they continue treatment. We are seeking the broadest possible participation from couples who are considering NPT treatment. Data from all couples will be useful for this study, regardless of their individual circumstances or actual treatment.

Page numbers from a sponsor's protocol/grant may be referenced in 2b and 2c.

Protocol Title: Natural Procreative Technology Evaluation and Surveillance of Treatment for Infertility and Miscarriage

b) List your research objectives (specific aims & hypotheses of the study).

This is an exploratory study rather than a hypothesis testing study. This study aims to determine what the live birth rates are over time for patients who are treated with natural procreative technology (NPT) for infertility or history of spontaneous abortion, and how the live birth rate may vary by patient characteristics, especially the age of the woman, prior pregnancy, and underlying diagnoses. Secondary analyses will explore outcomes of conceptions (live birth versus other outcomes) and the association of environmental exposures with infertility. This is an observational study: there will be no intervention. Patients will receive whatever care they choose to receive. Couples receiving NPT treatment will be compared to those declining NPT treatment, waiting for NPT treatment, receiving other treatment, or stopping treatment. Interventions received, conceptions, and outcomes of conceptions will be followed for up to 3 years for each couple entering the study.

Please save frequently

c) Describe the study design (e.g., single/double blind, parallel, crossover, control, experimental, observational, etc.). If the study is investigator-initiated, a timeline for individual subject recruitment, follow-up, and analysis for the study is required. Also, indicate if the subjects will be randomized.

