The Woman's Entrance Questionnaire will be completed by the subject at the time of their initial visit or as soon as possible per SOC. Following enrollment into the study, the subject will complete the following questionnaires:

- Women's Update Questionnaire on an annual basis (from the date of completion of the Women's entrance questionnaire) for up to 3 years (research related),
- Pregnancy Outcome Questionnaire for any pregnancy (research-related),
- Women's Exit Questionnaire whenever they exit the study (research-related).

Depending on the timing of subject enrollment, any follow-up questionnaire time point which may have already occurred at the time of subject enrollment will be considered skipped. Questionnaires may be done by mail, email or telephone. Each questionnaire will take approximately 30-45 minutes to complete.

For male partners:

The Men's Entrance Questionnaire will be completed per SOC (may be completed before or after enrollment into the study).

Following enrollment into the study, the subject will complete the following questionnaires:

- Men's Update Questionnaire on an annual basis (from the date the female partner completed the Women's entrance questionnaire) for up to 3 years (research-related),
- Men's Exit Questionnaire whenever they exit the study (research-related).

Depending on the timing of subject enrollment, any follow-up questionnaire time point which may have already occurred at the time of subject enrollment will be considered skipped. Questionnaires may be done by mail, email, or telephone. Each questionnaire will take approximately 30-45 minutes to complete.

- 2) The subject's own Creighton Model fertility charts. (The Creighton Model Fertility charts teaches couples to recognize, understand, and record the changes that occur during the fertility [menstrual] cycle. These changes [biomarkers] indicate whether the reproductive system is functioning normally or not. It also identifies ovulation and other key events. It is completely natural and cooperative with a woman's fertility [menstrual] cycle).
- 3) Information about NPT treatment and pregnancies from the medical records of their NPT physician(s) (prospective and/or retrospective, based on the timing of consent)..

This data collection will continue for up to three years after enrollment into the study (research related).

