We will keep track of all information, including information needed to contact the subject at the Study Center at Saint Louis University. All information will be kept confidential. No personal information will be released to anyone outside the study.

The study database has been constructed without any patient identifiers (no name, address, phone number, or identification numbers other than study subject number). The subject's contact information will be kept separate from the study data.

Protocol Title: Natural Procreative Technology Evaluation and Surveillance of Treatment for Infertility and Miscarriage

Combined results will be used for the analysis in this study. It will be impossible to identify any individual during the course of the analysis or in the reporting of the results.

Couples presenting for possible treatment with NPT will be recruited for participation in the study. Observation of the characteristics of the couples, the nature of the NPT treatments, and the outcomes including live births will be followed for up to 3 years for each couple entering the study.

The paper informed consent form will be reviewed with the couple in detail in the office. Individuals will have the opportunity to ask questions before they consent.

Follow up Questionnaires may be completed per the patient's preference, by e-mail, phone or in person.

All data collected (no PHI) from the questionnaires and medical records will be entered into a single secure database that will be kept at the Saint Louis University, Department of Ob, Gyn and Women's Health.

- c) If the proposed study is a clinical trial where a drug, vaccine, device or other treatment is compared to a placebo group or comparison treatment group, what are the guidelines or endpoints by which early decisions regarding efficacy or lack of efficacy can be made? For example, it may be reasonable to stop enrollment on a study when efficacy has already been clearly demonstrated, to avoid unnecessary enrollments of additional subjects. Alternatively, it may be reasonable to stop enrollment when it is clear that efficacy will never be demonstrated, given the statistical power of the study as designed. Describe the guidelines that are in place to assist in making these determinations, if relevant to the proposed study.

NA

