- d) Describe how data analysis will be performed (statistical tests, methods of evaluating data) and indicate the smallest group/unit for which separate reporting will occur. For studies involving a questionnaire, if data and reliability information are available, please describe or provide references. For full board, unfunded studies describe sample size determination and power analysis. If none, please justify.

The database exists in Microsoft Access. Analyses will be done in Excel (for basis of descriptions), SAS and/or SPSS statistical computer programs. As stated above, data used in the analysis will be aggregate data, and will not contain any individual identifiers. Therefore, there will be no possibility of identifying individual respondents during the analysis or in the reporting of the final results.

Analysis of Main Outcome

The main outcome of this study is the proportion of subjects that had a live birth at various time points up to five years after beginning treatment with NPT, compared to couples who do not receive NPT treatment, or who cease to receive NPT treatment. This will be analyzed by standard lifetable techniques to deal with censored data (i.e., couples for whom pregnancy status cannot be ascertained beyond a certain time period). Cox proportional hazards regression will be used in an exploratory manner to investigate demographic and medical characteristics (particularly woman's age, prior pregnancy, and associated medical diagnoses) that may be associated with a greater likelihood of successful live birth. The same set of analyses will be repeated for the secondary outcome of conception (clinical pregnancy).

Analysis of Secondary Outcomes

Initially, all secondary outcomes will be analyzed as simple proportions, e.g., of couples who conceived, what proportion had a live birth, spontaneous abortion, or other pregnancy outcome.

Protocol Title: Natural Procreative Technology Evaluation and Surveillance of Treatment for Infertility and Miscarriage

conceived, what proportion had a live birth, spontaneous abortion, or other pregnancy outcome. Where indicated by the initial analysis, supplementary analyses using standard statistical techniques may be employed (e.g., a logistic regression with the outcome of live birth versus other pregnancy outcome).

Sample Size

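### The main outcome compares NPT with no NPT up to five years, but each couple is followed for at most three years and never-NPT couples have no time zero

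*Combined protocol and SAP*

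**What the plan says.** The Analysis of Main Outcome in section 3d sets the endpoint as the "proportion of subjects that had a live birth at various time points up to five years after beginning treatment with NPT". It adds the comparison: "compared to couples who do not receive NPT treatment, or who cease to receive NPT treatment". The method is a life table with censoring, followed by exploratory Cox regression. The same analyses are to be repeated for conception.

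The rest of the protocol gives a three-year limit:

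- Section 2a: "Couples will be followed for up to three years, regardless of when they begin NPT treatment, or whether they continue treatment".
- Section 2b: "Interventions received, conceptions, and outcomes of conceptions will be followed for up to 3 years for each couple entering the study".
- Section 3b, on data collection: "This data collection will continue for up to three years after enrollment into the study (research related".
- Section 3b, later: "the outcomes including live births will be followed for up to 3 years for each couple entering the study".
- Sections 2c and 8k and the justifications under expedited categories 5 and 7 also give three years.

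Section 2b names the groups to be compared: "Couples receiving NPT treatment will be compared to those declining NPT treatment, waiting for NPT treatment, receiving other treatment, or stopping treatment". Two provisions let NPT start before enrollment. Section 13 allows consent at the first consultation or at a later visit, and section 3b allows retrospective records depending on when consent was given.

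**The concern.** The stated horizon is two years longer than the follow-up, and no part of the protocol reconciles them. There is no extension, registry linkage or later contact.

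The clock is the second difficulty. Time is counted from NPT start, yet one comparison group by definition never starts NPT, and section 3d gives it no other origin.

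A four- or five-year result could therefore be reported as a comparison when nobody was at risk on the no-NPT side. On the NPT side it would come only from couples already under NPT before they consented. With 45 women enrolled and analysis and manuscript work under way (continuing review form, items 7 and 13), a reader could not see this unless numbers at risk were shown.

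**Working it through.** The plan gives no sample-size, event or power figure to reproduce. The check is arithmetic on observation windows.

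**Inputs.** Horizon H = 60 months from NPT start (3d). Follow-up F = 36 months after enrollment (3b). First IRB approval 01/20/2016 (continuing review form, item 2); the Event History shows the new form approved on 02/17/2016. Follow-up is reported complete (item 13) on a form submitted 12/10/2019 (Event History).

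**Gap.** H − F = 60 − 36 = 24 months, and 24/60 = 40% of the stated horizon.

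**Couples who never receive NPT.**
- NPT-start clock: no origin, so no time at risk at any point.
- Enrollment clock: time at risk ends at 36 months, so none in months 36–60.

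**Couples who receive NPT, including those who later stop.** Let p be months of NPT before consent (negative if NPT starts after enrollment). On the NPT-start clock, with entry to the risk set at consent, the window runs from max(0, p) to 36 + p. The values of p are illustrative.

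| p (months) | Window (months from NPT start) | Contribution to months 0–36 | Contribution to months 36–60 |
|---|---|---|---|
| −12 | 0–24 | 24 | 0 |
| 0 | 0–36 | 36 | 0 |
| +12 | 12–48 | 24 | 12 |
| +24 | 24–60 | 12 | 24 |
| +36 | 36–72 | 0 | 24 |

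Passing month 36 needs p > 0. Reaching month 60 needs p ≥ 60 − 36 = 24. Retrospective records may add earlier time but do not move the upper end. On the enrollment clock no couple in any group passes month 36.

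**Calendar, as a secondary check.** From 01/20/2016 to 12/10/2019 is 1,420 days, or 46.7 months (1,392 days, 45.7 months, from 02/17/2016). Both are below 60. So even without the three-year limit, no couple starting NPT at or after enrollment could have reached month 60. Reaching it by 12/10/2019 needs NPT begun by 12/10/2014, which is 13.3 months before 01/20/2016.

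**The case against.** The strongest reply is that the wording sets a ceiling, that life tables are built for unequal follow-up, and that the study calls itself exploratory and makes no power claim. Part of this stands: estimates through year 3 are intact. But censoring helps only while someone remains at risk. With nobody at risk in the never-NPT group after month 36, its curve has no estimate there without extrapolation.

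A second reply is that late consent and retrospective records carry some couples past year 3. That is true for NPT couples, as the table shows. A reader might infer from the conflict that nobody can be observed after year 3, or that the main outcome cannot be estimated at all. The documents support neither. A reader might also infer that late NPT estimates are biased in a known direction, because they rest on couples still attending the practice. The documents do not establish a direction.

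A third reply is that other clocks exist. On a clock from first consultation or from the entrance questionnaire, a never-NPT couple who consented late could have record data past year 3. Section 3d names no such clock, so the conclusion here is confined to the NPT-start and enrollment clocks.

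The 19-year study total in section 8k might suggest longer follow-up. It is reached by adding 10 + 3 + 3 + 3, which counts couple involvement and data collection per couple as separate periods. Section 3b excludes that reading by ending data collection three years after enrollment.

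**Conclusion.** The point holds and should be fixed. Section 3d states a comparison horizon that the design cannot deliver. On the NPT-start or enrollment clock, the comparison with never-NPT couples cannot be estimated for years 3 to 5. On the NPT-start clock as written, those couples do not enter the analysis at all.

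Any NPT estimate after month 36 from NPT start rests solely on couples who began NPT before consent, and at month 60 on those who began at least 24 months before. How many there are is unknown.

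The window results assume that the section 3b limit of three years from enrollment applies to every couple. The calendar check further assumes that nobody consented before first IRB approval and that follow-up ended no later than submission of the 12/10/2019 form. The practical weight is moderate: the three-year results survive, and the remedy needs no new data collection.

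**What to change.** Revise section 3d as follows, labelled as a change made after data collection because follow-up is reported complete.

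1. **Comparison.** Limit it to 36 months from one origin available to all groups, for example the woman's enrollment date. Classify couples by NPT status as it changes over time (not started, on NPT, stopped), so that time before starting NPT is not credited to NPT.
2. **Description of NPT-treated couples.** Keep time from NPT start. Couples who began NPT before consent enter the risk set at consent. Show estimates beyond month 36 only with numbers at risk and a note that they rest solely on couples already on NPT before consent.
3. **Reporting.** Give numbers at risk by group at 12, 24 and 36 months.

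**Costs.**
- The comparison horizon is two years shorter.
- Numbers near month 36 may be small: anyone enrolled after 12/10/2016 cannot have 36 months by 12/10/2019, and enrollment dates are not given.
- Annual questionnaires run from the entrance questionnaire, not from enrollment (3b). If a woman consented 24 months after hers, for illustration, scheduled updates would cover only 36 − 24 = 12 months after enrollment. Ascertainment would then rest mainly on charts and records, and the report should say so.
- The change needs dated NPT starts and stops. The abstraction forms and questionnaires are listed in section 16 but cannot be seen here.

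How to treat NPT status at conception and pregnancies already under way at consent is a separate matter that this change does not settle.
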